1. OBJECTIVES

The overall objective of this study is to develop, and pilot test a novel regimen of psilocybin-assisted psychotherapy for demoralization in patients receiving hospice care.

1.1 Study Design

Open label, single center, concurrent mixed-methods phase 2 pilot trial of a single dose of psilocybin for demoralization in patients receiving hospice care.

1.2 Primary Objectives

To assess, using quantitative and qualitative measures, the feasibility of delivering a single dose of psilocybin 25 mg under supportive psychotherapeutic conditions to patients with moderate-to-severe demoralization (Demoralization Scale-II \geq 8) who receive hospice care at home.

Hypothesis:

Treatment and week 1 assessments will be successfully completed in at least 60% of recruited subjects, and \geq 80% of subjects who completed Week 1 assessment will evaluate favorably acceptability.

1.3 Secondary Objectives

To explore the safety of psilocybin-assisted therapy in this population and its preliminary efficacy on demoralization and other patient-reported and family caregiver-reported outcomes.

Hypotheses:

No serious adverse-event related to the intervention will occur and week 1 outcomes assessment will show improvement in demoralization.

2. BACKGROUND

2.1 Study Disease(s)

Terminal illness related to cancer and non-cancer diagnoses.

2.2 IND Agent

The IND agent, psilocybin, is manufactured by Usona Institute, a 501(c)(3) non-profit medical research organization that obtained Breakthrough therapy status from the Federal Drug Administration (FDA) for its Current Good Manufacturing Practice (cGMP) psilocybin in the treatment of Major Depressive Disorders (IND 129532).

Psilocybin (3-[2-(dimethylamino)ethyl]-1H-indol-4-yl] dihydrogen phosphate) is a natural product produced by numerous species of Psilocybe mushrooms, which is

manufactured for clinical use to control potency and purity. It is a tryptamine derivative, and in humans the phosphate group is rapidly enzymatically cleaved in the body to produce psilocin, an agonist at a variety of serotonin receptors, the most important of which in this setting is the 5-HT2A receptor. Oral psilocybin has about a 50% bioavailability and psilocin is detectable in plasma within 20 minutes of administration of the parent compound. He half-life of psilocin in blood is 2-3 hours. Onset of noticeable psychoactive effects occurs within one hour, peaks at about two hours after a dose, and loss occurs typically around six hours after the dose. Based on this time course, in the clinical trial setting, protocols mandate observation until approximately 8 hours after dosing.

Psilocybin reliably induces profound changes in sensory perception, emotion, thought, and sense of self, characterized by marked alterations in all mental functions, including perception, mood, volition, cognition and self-experience.^{5,6} These profound changes are often referred to as mystical-type experiences. Measures of mystical-type experience occurring during psilocybin treatment have been repeatedly observed to predict later effects on behavior and emotions, including reductions in depressive and anxious symptoms.^{7–9}

Non-clinical in vivo and in vitro studies, found via literature searches, demonstrate that similar to humans, when psilocybin is administered orally to rats it is rapidly dephosphorylated to psilocin in the intestinal mucosa by alkaline phosphatase and a nonspecific esterase, with approximately 50% of the total volume of psilocin absorbed from the digestive tract. Maximum plasma levels are achieved after approximately 90 minutes. When administered systemically (i.e., bypassing the gut), initial psilocybin metabolism is performed by tissue phosphatases, with in vitro studies indicating the kidneys as being among the most active metabolic organs. Across species tested, the highest levels of psilocin were found in the neocortex, hippocampus, and thalamus.

Recent clinical studies utilizing pharmaceutical-grade oral psilocybin under controlled conditions have been performed upon healthy participants and various subpopulations in order to gauge safety events and preliminary clinical efficacy. Though the safety reporting criteria and the level of data verification varied greatly between studies, including many participant-reported outcomes, these data have been utilized to elucidate the expected adverse event (AE) profile of psilocybin. The clinical studies summarized in the investigator brochure present similar safety profiles, with both psychological and physical adverse events reported. The most common adverse psychological events included transient anxiety, negative emotional states and paranoid/delusional thinking during dosing sessions, and the most common physical effects were increased blood pressure (BP) and heart rate, mild nausea, and mild headache.

Preliminary efficacy of psilocybin in these studies showed a substantial and sustained decrease in symptomatic response in indications including obsessive compulsive disorder (OCD), substance use disorder, depression, anxiety, and psychological and existential distress in patients with serious illness (e.g. cancer). Overall, psilocybin has been well-tolerated at the doses examined in the clinic. Due to the psychoactive nature of the compound, it should only be administered in a controlled setting and per the accompanying clinical protocol.

Psilocybin is currently under phase 2b of drug development in patients with depression and treatment-resistant depression (NCT03866174 and NCT03775200 respectively), and if the outcomes are positive, then it seems plausible that psilocybin will become a licensed medicine for a range of indications in psychiatry and serious illness care when used in an approved treatment model.¹³ In the past few years, many renowned academic medical centers in the United States have (re)started investigating the clinical applications of psilocybin, among which John Hopkins University School of Medicine, New York University, Harbor-UCLA, and more

2.3 Rationale

Version Date: April 18, 2023

recently Yale, Mass General Hospital and Berkley.

More than 1.4 million Americans receive hospice care each year, of whom 30% have a principal diagnosis of cancer. For most of these patients and families, emotions such as fear, anger or sadness are common and normal. However, 38 to 50% of patients experience clinically relevant anxiety and/or depression that significantly impacts their and their caregivers quality of life (QOL). High quality hospice care ought to seek, as a fundamental goal, to address this psychological distress. Yet, symptoms such as depression are often underrecognized and undertreated in this population. This may be due to clinicians or patients not recognizing depressive symptoms in the context of serious illness, 17–19 to the lack of effective treatment, 20–22 or both. In addition, existential suffering, commonly experienced at the end of life and manifested through demoralization syndrome, exacerbates anxiety and depression. Among the management of these symptoms would benefit healthcare outcomes of millions of patients and family caregivers, and society at large.

Psilocybin-assisted therapy presents a novel potential therapeutic modality for hospice patients, as preliminary evidence suggests its safety and efficacy to treat psychosocial distress in people with serious illness. ^{8,9,27–30} Psilocybin is a serotoninergic psychedelic derived from a class of fungi. Based on therapeutic models developed in the 1960s, this drug-facilitated psychotherapy combines an inner-directed psychotherapy to the consciousness-expanding properties of psilocybin, by agonism of the serotonin receptor 5HT2A, to facilitate the processing and resolution of psychological and existential issues. ^{1,31–34} In patients with cancer, recent double-blind, randomized controlled trials of psilocybin-assisted therapy showed pronounced and prolonged reductions in depression and anxiety, as well as sustained benefits in existential distress, spiritual well-being and quality of life. ^{8,9,27}

Grob et al.'s study included 12 patients and demonstrated the safety and feasibility of administering psilocybin-assisted therapy within cross-over randomized controlled trials in this setting.²⁷ Using similar designs in larger sample sizes, Griffith et al.'s and Ross et al.'s studies further documented safety and feasibility, and demonstrated rapid, robust and sustained improvements of depression and existential distress in cancer patients. In particular, Griffith et al.'s study found sustained remission of depression symptoms at 6 months in 70% of patients (n=51)⁸ and Ross et al.'s study found enduring antidepressant and anxiolytic effect following psilocybin administration in 80 and 60% of patients respectively (n=29).⁹ In the latter study, 3.2 and 4.5 years follow-up showed continued reductions in depression or anxiety, sustained benefits in existential distress and quality of life, and improved attitudes towards death anxiety in most

patients.²⁸ Following these results, the FDA approved two large multicenter confirmatory trials in non-cancer patients with MDD and treatment resistant depression (TRD) respectively.^{35,36}

Another study conducted by Anderson et al. and recently published in EClinicalMedicine provides useful background for our study.³⁷ This open-label study assessed the safety and feasibility of psilocybin-assisted group therapy for demoralization in 18 older long-term AIDS survivor (OLTAS) men, a population of patients with serious illness with particularly complex medical and psychiatric needs. Findings demonstrated a clinically meaningful change in demoralization from baseline to 3-month follow-up. Zero serious adverse reactions and two unexpected adverse reactions to psilocybin were detected, and seven participants experienced self-limited, severe expected adverse reactions (see adverse events table in section 7.1).

Psychedelic-assisted therapies raise both excitement and concern among key stakeholders in serious illness care. ^{38,39} Our group conducted in-depth interviews of experts involved in serious illness care and/or psychedelic research that highlighted the need to conduct rigorous psilocybin trials in the context of interdisciplinary psychosocial and palliative care. ³⁹ Rapid evolution in the legal and regulatory status of psychedelics has heightened the urgency of obtaining scientific evidence to inform future standards of care for psychedelic-assisted therapies. ^{13,40,41} This is particularly true for patients with cancer receiving hospice care, who may derive substantial benefit and yet may have particular vulnerabilities.

To date, no study has assessed the safety and efficacy of psilocybin-assisted therapy to address psychosocial, existential, or spiritual distress in patients with a terminal illness receiving hospice care. Defining relevant eligibility criteria and treatment regimen is critical for patient safety. Conducting rigorous randomized controlled studies in this population presents unique challenges, warranting feasibility studies that carefully prepare larger confirmatory trials. To bridge this gap, our Department has partnered with Care Dimensions, a non-profit leader in hospice care and the largest hospice organization in Massachusetts. Our group is uniquely equipped and positioned to deliver, assess and refine this novel intervention. This study, by pilottesting a new model of psilocybin-assisted therapy in patients receiving hospice care, will facilitate the success of future randomized multi-center trials necessary to confirm the intervention's efficacy in this patient population and shape the therapeutic model. Given the unmet need in this large population of patients and family caregivers, the potential to positively impact healthcare outcomes in the field is high.

3. PARTICIPANT SELECTION

3.1 Eligibility Criteria

Version Date: April 18, 2023

- 3.1.1 Patients enrolled in hospice care at home
- 3.1.2 Age \geq 21 years.
- 3.1.3 Any terminal illness with respect of exclusion criteria
- 3.1.4 Palliative Performance Scale (PPS) \geq 40 % (see Appendix A)
- 3.1.5 Moderate-to-severe demoralization as measured by Demoralization Scale-II \geq 8 (see Appendix A)
- 3.1.6 Significant other or other caregiver present at home the night of study drug administration
- 3.1.7 No driving for 24 hours following study drug administration.
- 3.1.8 English proficiency
- 3.1.9 Ability to understand and the willingness to sign a written informed consent document.
- 3.1.10 Psilocybin is very likely to have no genotoxic effects. One study that directly focused on the mutagenic potential of psilocybin did not found this type of toxicity. 42 However, due to the lack of clinical and non-clinical studies on the effects of psilocybin on the developing human fetus, women and men of child-bearing potential and who are sexually active must agree to use an acceptable contraceptive method (hormonal or barrier method of birth control; abstinence) throughout their participation in the study. Should a woman become pregnant or suspect she is pregnant while she or her partner is participating in this study, she should inform her treating physician immediately. Men treated or enrolled on this protocol must also agree to use adequate contraception prior to the study, for the duration of study participation, and 4 months after completion of psilocybin administration.
- 3.1.11 Patients with first-degree relatives with schizophrenia or bipolar disorder may be eligible depending on their age and personal and family psychiatric history. The decision will be made by the principal investigator and study psychiatrist based on risk assessment.

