3.2 Exclusion Criteria

- 3.2.1 Current General Inpatient (GIP) hospice status
- 3.2.2 Patients currently receiving chemotherapy
- 3.2.3 Condition impairing oral intake or digestive absorption
- 3.2.4 Presence of a delirium diagnosed by the CAM (see Appendix A)
- 3.2.5 Significant suicide risk as defined by suicidal ideation with intend and a plan as endorsed on item 5 on the C-SSRS within the past month or at V0 (see Appendix A)
- 3.2.6 Current or past history of schizophrenia, psychotic disorder, bipolar disorder, delusional disorder, paranoid personality disorder, schizoaffective disorder, or borderline personality disorder, as assessed by medical history
- 3.2.7 History of allergic reactions attributed to compounds of similar chemical or biologic composition to psilocybin
- 3.2.8 Other personal circumstances and behavior that would limit compliance with study requirements, or judged by the study psychiatrist and/or principal investigator to be incompatible with establishment of rapport or safe exposure to psilocybin
- 3.2.9 Potential for adverse drug-drug interactions. Concomitant medications with significant potential to interact with study medications will be exclusionary if they cannot be tapered. These include the following:
 - Serotoninergic antidepressants
 - Centrally-acting serotonergic agents (e.g. MAO inhibitors)
 - Antipsychotics (e.g. first and second generation)
 - Mood stabilizers (e.g. lithium, valproic acid)
 - Aldehyde dehydrogenase inhibitors (e.g. disulfiram)
 - Significant inhibitors of UGT 1A0 or UGT 1A10

Any psychiatric medication will be tapered if possible in an appropriate fashion to avoid withdrawal effects. They will be discontinued long enough before the psilocybin Session to avoid the possibility of any drug-drug interaction (the interval will be at least five times the particular drug and active metabolites' half-life). See section 9 of the protocol for concomitant medications and tapering instructions.

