5.2. Pre-Treatment Criteria

5.2.1. Cycle 1, Day 1

- Vital signs in the normal range
- Palliative Prognosis Score ≥ 50 %
- No significant suicide risk
- No delirium
- No contra-indicated medication

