Psilocybin is contraindicated in participants who are on monoamine oxidase inhibitors or who have a known sensitivity to the drug or its metabolites. It is contraindicated in medications that are known uridine diphosphate glucuronosyltransferase enzyme modulators. It is contraindicated in patients with schizophrenia or bipolar disease, or in those with first degree relatives with these disorders. The concurrent use of selective serotonin reuptake inhibitor/serotonin-norepinephrine reuptake inhibitors (SSRI/SNRI) medications is assumed to be contraindicated due to the potential to increase the risk of serotonin syndrome and/or to attenuate the binding of psilocin to the HT2A receptor.

Prior to enrollment participants will be screened per the clinical protocol for contraindicated psychologic conditions or interacting medications by a licensed physician on the study team.

Because there is a potential for interaction of psilocybin with other concomitantly administered drugs through the cytochrome P450 system, the study team will review the concurrent use of all other drugs, over-the-counter medications, or alternative therapies at every visit. The PI should be alerted if the participant is taking any agent known to affect or with the potential to affect selected CYP450 isoenzymes. Appendix C presents guidelines for identifying medications/substances that could potentially interact with the study agent(s).

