13. STATISTICAL CONSIDERATIONS

13.1. Primary outcome variables

This study is an open label, single center, concurrent mixed-methods phase 2 trial. The primary objective is to pilot test a novel protocol of psilocybin-assisted therapy in patients receiving hospice care. Primary outcomes will relate to the following features of feasibility:

[figure not shown]
• **Enrollment:** number screened per month; number enrolled per month; average time delay from screening to enrollment

- **Retention:** number of sessions completed; retention rates for study measures; reasons for dropouts
- Completion of assessment: proportion of planned assessments that are completed; duration of assessment visits; reasons for dropouts
- Acceptability: acceptability ratings; qualitative assessments; reasons for dropouts

Benchmark for feasibility: treatment and week 1 assessments will be successfully completed in at least 60% of recruited subjects.

Benchmark for acceptability: $\geq 80\%$ of subjects who completed Week 1 assessment will evaluate favorably (agree or strongly agree) acceptability on the global evaluation factors of the RRPQ (See section 5.1)

To guide our evaluation of acceptability in the proposed project, we will use seven component constructs as defined in the following figure: affective attitude, burden, ethicality, intervention coherence, opportunity costs, perceived effectiveness and self-efficacy.⁷²

Theoretical framework of acceptability (from Sekhon et al., 2017)

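### Section 3.1.11 lets patients with a first-degree relative with schizophrenia or bipolar disorder be admitted at discretion, while section 5.4 calls psilocybin contraindicated in that group without exception

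*Combined protocol and SAP*

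**What the plan says.** Section 3.1 (Eligibility Criteria), item 3.1.11, deals with family history directly: "Patients with first-degree relatives with schizophrenia or bipolar disorder may be eligible depending on their age and personal and family psychiatric history". It then names who decides and on what basis: "The decision will be made by the principal investigator and study psychiatrist based on risk assessment".

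Section 5.4 (General Concomitant Medication and Supportive Care Guidelines) lists when psilocybin is contraindicated. On psychiatric history it says: "It is contraindicated in patients with schizophrenia or bipolar disease, or in those with first degree relatives with these disorders". The next paragraph sets the time of the check: "Prior to enrollment participants will be screened per the clinical protocol for contraindicated psychologic conditions or interacting medications", to be done by a licensed physician on the study team.

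Two other places bear on the matter. Exclusion criterion 3.2.6 begins "Current or past history of schizophrenia, psychotic disorder, bipolar disorder, delusional disorder, paranoid personality disorder" and goes on to further diagnoses, all as the patient's own history. The dosing-day list in 5.2.1 includes the item "No contra-indicated medication" but has no item on family history.

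**The concern.** Sections 3.1.11 and 5.4 address the same relatives and the same two diagnoses. One makes entry a matter of individual judgement; the other is categorical. Both are current body text.

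What is at stake is who may receive a psychoactive study drug. The protocol treats psychiatric risk as central. Its rationale (2.3) describes well-defined eligibility criteria as critical to patient safety. Section 7.2.1 lists paranoid or delusional thinking among the expected adverse events. Section 7.4.4 exempts related psychosis and delusions of grades 1 to 3 from expedited reporting to the IRB as long as they follow the expected course of the drug effect. With those provisions in place, the rule on familial psychiatric risk should have only one reading.

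There is a practical side too. Under 4.1 an investigator confirms eligibility and a member of the team completes a protocol-specific checklist. A checklist built from section 3 and one built from 5.4 would classify the same patient differently.

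**Working it through.** No sample size, rate or interval enters this point, and the plan gives no figure to reproduce. The check is a comparison of the relevant sections.

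| Section | Whom it covers | Rule | Exception or cross-reference |
|---|---|---|---|
| 3.1.11 | Patients with an affected first-degree relative | Entry possible, decided case by case | Names the deciders and the basis; does not mention 5.4 |
| 5.4 | Patients with either disorder, and patients with an affected first-degree relative | Psilocybin contraindicated | None; does not mention 3.1.11 |
| 3.2.6 | Patients with their own current or past history of the listed disorders | Excluded | Relatives not mentioned |
| 5.2.1 | Every patient on the dosing day | Vital signs, performance score, suicide risk, delirium, contraindicated medication | Family history not listed |
| 5.5 | Patients on protocol therapy | Reasons for halting treatment | Family history not named |

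1. **Is it the same group?** Yes. Both 3.1.11 and 5.4 speak of first-degree relatives, and both name schizophrenia and bipolar disorder (5.4 writes bipolar disease).

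2. **Are the rules different?** Yes. Under 3.1.11 some of these patients can enter. Under 5.4 the drug is contraindicated in all of them.

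3. **Does another section settle it?** No. Section 3.2.6 concerns the patient's own history, so it conflicts with neither rule and resolves nothing. No section states an order of precedence.

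4. **What follows if 5.4 governs?** Its check comes before enrollment, so every such patient is turned away at screening. The decision that 3.1.11 gives to the investigator and the psychiatrist then never arises.

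5. **What follows if 3.1.11 governs?** The reference in 5.4 to screening under the clinical protocol could be read as pointing back to section 3. A patient admitted on a favourable risk assessment would then receive a drug that 5.4 says is contraindicated for that patient.

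6. **Would a later step catch it?** Not by name. Neither 5.2.1 nor 5.5 asks about relatives.

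7. **Is family history unusual within 5.4?** Yes. The other contraindications there have at least a partial counterpart among the exclusions: 3.2.9 for interacting drugs, 3.2.7 for sensitivity, 3.2.6 for personal history. Family history has no matching exclusion and appears instead as a permissive item among the eligibility criteria.

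**The case against.** The best defence is that 3.1.11 is the operative rule. It is a numbered item in the participant-selection section, addresses exactly this group, and says who decides and how. Section 5.4 is mainly about concomitant medication and refers screening back to the protocol. In addition, 3.2.8 lets the same two roles exclude anyone for whom exposure to psilocybin is judged unsafe. An affected patient would therefore get an individual risk review, not unmanaged exposure. That is a fair description of the safeguards, and it tempers the concern. It does not remove the conflict: the protocol never says that 3.1.11 prevails, and 5.4 does not present its contraindication as relative or open to judgement.

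Some stronger readings are tempting, and the documents do not support them.

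- **That such patients will be enrolled and then refused the dose.** Section 5.4 places its check before enrollment, the V0 description in 5.1.1 admits only patients who meet every eligibility criterion, and no later step re-tests family history. Exclusion at screening or dosing under 3.1.11 are the likelier outcomes.

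- **That the primary feasibility rate is put at risk by a known amount.** The plan says "Benchmark for feasibility: treatment and week 1 assessments will be successfully completed in at least 60% of recruited subjects", and 15 patients are planned, so a reader might compute 1/15 = 6.7 percentage points per patient lost. That is the weight of any one non-completer for any reason. It would apply here only to a patient who was recruited, then withheld, and would otherwise have completed. The documents give no frequency for patients with an affected relative, and the number could be zero.

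- **That no one can comply with both sections.** Section 3.1.11 permits; it does not oblige. Declining every such patient satisfies both, although it leaves 3.1.11 without effect.

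**Conclusion.** The point holds as an internal inconsistency on a participant-safety rule. For one defined group, 3.1.11 grants a discretion that 5.4 contradicts, and the protocol does not say which prevails.

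The conclusion rests on the wording of the two sections and on the absence of any precedence statement in the documents. It needs no assumption about how often the situation arises or how staff would act. It is unquantified, and no effect on the feasibility or acceptability benchmarks is claimed. It should be corrected because it concerns who may be given the study drug, not because of any effect on the primary outcome. No view is taken on which of the two rules is clinically right.

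**What to change.** Reconcile 3.1.11 and 5.4 so that a single rule governs patients with an affected first-degree relative, with each section agreeing with or referring to the other. Put the same rule into the protocol-specific eligibility checklist used under 4.1. Amend 3.2.6 only if the chosen rule makes family history an exclusion; otherwise it can stand as written. The investigator and the study psychiatrist should choose the rule.

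The cost is an amendment to protocol wording and to one checklist. The sample size, the assessments and the analysis are unaffected.
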